 - c. Symptomatic or documented congestive heart failure that meets New York Heart Association (NYHA) Class III to IV definitions (see Appendix 6);
 - d. History of stroke within the last 6 months prior to screening

Inclusion of Women and Minorities

Both men and women of all races and ethnic groups are eligible for this trial.

Treatment Plan

Patients will be treated with TGR-1202 at a dose of 800 mg daily from day 1 to 28 on a 28-day cycle.

Duration of Treatment

Patients will be treated until one of the following events occurs:

- Disease progression
- Unacceptable adverse event(s)
- Withdrawal of consent
- Changes in the patient's condition that render continuation of the study drug unacceptable in the judgment of the treating physician
- An event that in the judgment of the treating physician warrants discontinuation of therapy.
- Patient withheld study drug for >28 days

Sample Size

The study will accrue a total of up to approximately **20 patients**.

Safety

Patients will be monitored carefully for the development of AE. AE will be evaluated according to criteria outlined in the National Cancer Institute (NCI) Common Terminology Criteria for Adverse Events (CTCAE), version 4.0.

Efficacy Outcome

Patients will be monitored for clinical and/or radiographic evidence of disease response. Response will be evaluated using clinical parameters, CT or PET/CT scan (PET/CT scan is preferred), and bone marrow or other tissue biopsy, according to the *Updated Recommendations for Evaluation, Staging, and Response Assessment for Hodgkin and Non-Hodgkin Lymphoma: The Lugano Classification.* (Cheson et al., 2014b)

Figure 1: Study Plan Flow Chart

[figure not shown]

Figure 2. Pharmacokinetics (PK) schedule

Pharmacokinetic studies

Cycle 1, days 1 and 15; cycle 2 , day 15; cycle 4, day 15

[figure not shown]
[figure not shown]

Figure 3. Pharmacodynamic (PD) Schedule

Pharmacodynamic studies on peripheral blood*

Cycle 1, days 1 and 15; cycle 2, day 15; cycle 4, day 15

Pharmacodynamic studies on tumor cells, blood cells, and buccal fibroblasts*

Screening, Cycle 2, day 15 (mandatory); cycle 4, day 15 (optional); end of treatment/POD (optional)

[figure not shown]
[figure not shown]

Figure 4. Study schema

¹ Includes tumor cells, blood cells, and buccal fibroblasts; tumor tissue includes nodal or extranodal tumor tissue that can be visualized and/or palpated + bone marrow aspiration and biopsy if bone marrow positive for lymphoma; ²

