5. TREATMENT PLAN

Regimen Description

Treatment will be self-administered on an outpatient basis. Patients will take TGR-1202 800 mg, one tablet daily on a continuous basis. Each cycle lasts 28 days. Reported adverse events and potential risks for TGR-1202 are described in Section 7. Appropriate dose modifications are described in Section 6. No investigational or commercial agents or therapies other than the study drug may be administered with the intent to treat the patient's malignancy.

Evaluation and requirements Prior to Each Treatment Cycle

Before the start of each treatment cycle, patients should be reassessed and the following criteria must be fulfilled:

- Absolute neutrophil count (ANC) $\geq 1,000/\text{dL}$
- Platelet count $\geq 50,000/\text{dL}$
- Serum creatinine concentration $\leq 2.0 \times \text{ULN}$ or $\leq \text{baseline}$, or creatinine clearance $> 50 \text{ ml/min}$
- AST (SGOT) and ALT (SGPT) $\leq 3.0 \times \text{ULN}$
- Bilirubin concentration $\leq 1.5 \times \text{ULN}$. Subjects with Gilbert's Syndrome may have a Bilirubin $> 1.5 \times \text{ULN}$ if no other cause of hyperbilirubinemia is present in the judgment of the treating physician; aPTT and PT not to exceed $1.2 \times \text{ULN}$
- Recovery of any drug-related non-hematological toxicity to Grade 2 or less, unless otherwise indicated

Guidelines for Administration of TGR-1202

- *Method of Administration:* TGR-1202 will be administered orally once daily with food □
- *Potential Drug Interactions:* No Drug Interactions have been reported to date.
- *Pre-medications:* Patients are required to start prophylaxis treatment with pneumocystis jiroveci pneumonia (PCP) and antiviral therapy within 7 days prior to randomization.
- *Anti-viral Prophylaxis:* Valtrex 500 mg daily or Acyclovir 400 mg BID or equivalent is recommended
- *PCP Prophylaxis:* Bactrim DS 1 tablet 3x per week or Dapsone 100 mg daily or equivalent is recommended.

Final choice of PCP and anti-viral prophylaxis therapy is per investigator discretion

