TGR-1202 will be dispensed at the sites by the research coordinator or designee under the direction of the PI or by a pharmacist at the site. Patients must be provided drug in its original container. Patients should be instructed to return any unused tablets when they return the bottle to the site. Study drug compliance should be reviewed with the patient at the beginning of each new treatment cycle and as needed. Missed doses will be documented in the patients' medical record.

TGR-1202 will be self-administered (by the patient). Tablets should be taken at approximately the same time each day with food. Patients should be instructed to swallow the tablets as a whole and should not chew or crush them.

If a dose of TGR-1202 is missed within 12 hours of its scheduled administration, the patient should take the dose. If it is missed more than 12 hours after the scheduled administration time, the patient should omit that dose and record in the diary. If vomiting occurs, no attempt should be made to replace the vomited dose.

Dispensing of TGR-1202

Before dispensing, the site pharmacist or his/her representative must check that the TGR-1202 is in accordance with the product specifications and the validity is within the re-test date.

The exact dose and the date of administration of TGR-1202 must be recorded within the case report form (CRF), patient's medical records. For the purpose of drug accountability and dosing, a drug diary will be utilized. Any error in drug administration should be recorded (e.g., missed dose) in the CRF.

The Pharmacist or his/her representative should record the date dispensed and patient's number and initials, as well as complete the accountability record in the electronic drug accountability system with information concerning the dispensation of TGR-1202.

Supportive care

Patients will be permitted to receive appropriate supportive care measures as deemed necessary by the treating physician including, but not limited to the use of anti-emetics, anti-diarrheal, antipyretics, anti-histaminics, analgesics, antibiotics, growth factors, blood products, and other drugs not prohibited during the study period.

- Use of myeloid growth factors and erythropoiesis-stimulating agents:

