8. PHARMACEUTICAL INFORMATION

A list of the adverse events and potential risks associated with the investigational or commercial agents administered in this study can be found in Section 7.2.

TGR-1202

[figure not shown]
Classification:	Phosphatidylinositol-3-Kinase (PI3K) Delta Inhibitor
Formulation:	See Investigator Brochure
Mode of Action:	Irreversibly inhibits activity of the Class I Delta isoform of PI3K
How Supplied:	TGR-1202: 200 mg tablets
Storage:	Store at 25°C. Excursions permitted 15°C to 30°C.
Stability:	Retest dates will be provided periodically by Sponsor.
Route of Administration:	Oral
Packaging:	TGR-1202 is provided in HDPE bottles each containing 30 tablets and a silica gel canister as a desiccant.
Availability:	TGR-1202 is available from TG Therapeutics.

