10. STUDY CALENDAR

Baseline evaluations are to be conducted as indicated in the table below, prior to start of protocol therapy. In the event that the patient's condition is deteriorating, laboratory evaluations should be repeated within 48 hours prior to initiation of the next cycle of therapy.

(All study assessments allow a +/- 3 day window)

Cycle		1				2+				
	Screening	D1	D8	D15	D22 ⁿ	D1	D15	End of treatment ^k	End of Study (4 weeks after last dose)	Follow-up ^m
Eligibility, safety monitoring, efficacy										
Informed Consent	X ^a									
Demographics	X ^a									
Medical History	X ^a									

EKG	X ^a								
Concurrent Medications	X ^b	X ^c	X	X	X	X		X	X
Physical exam	X ^b	X ^e	X	X	X	X		X	X
Vital Signs, weight	X ^b	X	X	X	X	X		X	X
Performance Status	X ^b	X	X	X	X	X		X	X
CBC w/ differential	X ^b	X ^e	X	X	X	X		X	X
Chemistries ^{c,g}	X ^b	X ^e	X	X	X	X		X	X
Coagulation tests	X ^b								
Creatinine clearance	X ^b								
Serum \square -hCG ^d	X ^b	X							
CT (or PET/CT)	X ^a					X ^f			X ^f
Bone Marrow Biopsy	X ^a					X ^o		X ^p	
Drug Administration									
TGR-1202 800 mg		X	→	→	→	→	→		
Toxicity Assessment		X	X	X	X	X		X	X
Correlative Studies									
Blood for PK		X ⁱ		X ⁱ			X ⁱ		
Blood for PD		X ^h		X ^h			X ^h		
Buccal swab	X ^l					X _{l,p}	X ^p		
Lymph Node/Bone Marrow Biopsy	X ^a					X _{l,p}	X ^p		

- a. To be done within 4 weeks of treatment start date.
- b. To be done within 1 week of treatment start date. Nurse practitioner can perform exams after cycle 1.
- c. Chemistries include: Chem *, Mg, K, Hepatic Function Panel, and LDH.
- d. To be done within 1 week of treatment start date for patients of childbearing age.
- e. Not necessary if conducted within 72 hours of screening assessment.
- f. CT scan of the neck, chest, abdomen, and pelvis (and/or PET/CT) at the end of Cycle 2 and 6. Thereafter, restaging CT scans will be repeated every 4 months, or every 6 months if a complete response is achieved. To be performed on every cycle.
- g. Sodium, potassium, chloride, calcium, and glucose are part of the electrolyte assessment at every time point.
- h. Pre-treatment on C1D1, and 4 hours post-treatment on C1D1, C1D15, C2D15 and C4D15
- i. Pre-treatment on C1D1, and 4 hours post-treatment on C1D1, C1D15, C2D15 and C4D15
- j. To be done within 4 weeks of treatment stop date.
- k. To be performed pre-treatment and 4-8 hours post-treatment on C2D15 (mandatory), and C4D15, end of treatment and progression of disease, if applicable (optional).

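### Section 5 describes the 800 mg daily dose as one tablet, but only 200 mg tablets are supplied, so four are needed; the pre-cycle blood-count units also need a check against the source file

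*Combined protocol and SAP*

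**What the plan says.** Section 5, Regimen Description, states: "Patients will take TGR-1202 800 mg, one tablet daily on a continuous basis". Treatment is self-administered by outpatients, and the same section tells them to take tablets whole, without chewing or crushing.

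Section 8, under How Supplied, gives one strength, "TGR-1202: 200 mg tablets", in bottles of 30. No 800 mg tablet appears anywhere in the documents.

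The dose in milligrams is the same throughout. The synopsis says "Patients will be treated with TGR-1202 at a dose of 800 mg daily from day 1 to 28 on a 28-day cycle"; the Section 10 calendar has "TGR-1202 800 mg"; the Section 6 dose-level table starts at 800 mg and steps down to 600 mg and 400 mg.

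Section 5 also contains controls on dosing. Before dispensing, the site pharmacist or a representative "must check that the TGR-1202 is in accordance with the product specifications". The exact dose and date go into the CRF. On the diary: "For the purpose of drug accountability and dosing, a drug diary will be utilized". On returns: "Patients should be instructed to return any unused tablets when they return the bottle to the site". Compliance is reviewed with the patient at the start of each cycle.

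Separately, the Section 5 requirements before each cycle are printed as ANC ≥ 1,000/dL and platelets ≥ 50,000/dL. The eligibility criteria in the synopsis and Section 3 use the same numerals with the unit spelled out as microliter.

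**The concern.** The faulty sentence is the operative description of how patients take the drug, so it is the one most likely to be copied into a diary, a patient handout or a dispensing instruction. If a site took the tablet count from it and the strength from Section 8, the patient would receive a quarter of the planned dose. Dose bears on the primary endpoint: Section 2 reports a strong exposure-response relationship in the phase I study. The same section also reports nodal reductions in CLL at any dose of the micronized formulation, so the documents give no basis for estimating how far a lower dose would reduce the response rate.

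The unit question concerns a binding rule. Section 6 says that the Section 5 criteria must be met before a new cycle can start. A limit printed 100,000 times too low would make the count check empty.

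**Working it through.** **Inputs.** Daily dose 800 mg (synopsis; Sections 5, 6 and 10). Tablet strength 200 mg and bottle of 30 (Section 8). Cycle of 28 days (synopsis, Section 5). Dose levels 800, 600 and 400 mg (Section 6). Pre-cycle limits 1,000 and 50,000 per dL (Section 5). Eligibility limits 1,000 and 50,000 per microliter (synopsis, Section 3).

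**1. The plan's own figure.** One tablet a day gives 800 mg only if the tablet contains 800 mg. With the listed strength, 1 × 200 mg = 200 mg. The plan's count does not reproduce.

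**2. The correct count.** Tablets per day = dose / strength = 800/200 = 4. Per cycle: 4 × 28 = 112 tablets, or 112/30 ≈ 3.7 bottles.

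**3. The count as worded.** 1 × 28 = 28 tablets per cycle. Fraction of the intended dose: 200/800 = 0.25.

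**4. Is the count wrong, or the strength?** The reduction levels settle it. With 200 mg tablets, 600/200 = 3 and 400/200 = 2, both whole numbers. A single 800 mg tablet swallowed whole can deliver neither 600 mg nor 400 mg. So the strength in Section 8 fits the rest of the protocol, and the count in Section 5 is the error.

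**5. Blood-count units.** 1 dL = 100,000 microliters.
- ANC as printed: 1,000/100,000 = 0.01 per microliter, against 1,000 per microliter in eligibility.
- Platelets as printed: 50,000/100,000 = 0.5 per microliter, against 50,000 per microliter in eligibility.

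**6. Effect on the design.** Section 13 gives 20 patients, a null ORR of 0.33, an alternative of 0.60, one-sided alpha of 0.10 and power of 87%. The exact binomial test that rejects at 10 or more responses has alpha 0.087 and power 0.872, so the stated power reproduces. Neither the tablet count nor the laboratory limits enter that calculation.

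**The case against.** The strongest reply is that this is an editorial slip. The sentence itself states 800 mg, every other statement of the dose agrees with it, and Section 8 gives the reader what is needed to work out four tablets. The controls in Section 5 make a persistent error unlikely. Most of this stands: the planned dose is clear, and the point is about wording. But the wording sits in the dosing instruction for a drug taken at home, and no section states the right count, so it deserves a correction that a typing error in the background would not.

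On the units, a colleague could fairly say that dL may be a microliter symbol misread in conversion. Symbols fail elsewhere in this text: stray boxes appear in Section 5 and before hCG in the Section 10 calendar, and in Section 2 the same kinase is spelled CK1 epsilon in one place and printed as CK1 α in another. This objection stands in full, and is why the unit point is conditional.

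Three stronger readings are tempting, and the documents do not support them.
- **Patients will be underdosed.** The diary, CRF and pharmacy instructions are not in the documents, so whether they repeat the wrong count is unknown, and the Section 5 checks work against it.
- **Returned tablets would expose the slip within a cycle.** The protocol does not state how many tablets are dispensed. If four full bottles were given and one tablet a day taken, 120 − 28 = 92 would come back. If a site followed the wording and gave one bottle, 30 − 28 = 2 would come back and look normal. Both quantities are assumptions, so no reassurance can be drawn from returns.
- **Section 6 leaves it open which rule governs when a cycle is due, because its table maintains the dose at some low counts.** Section 6 does settle this: the Section 5 criteria are mandatory for starting a cycle and the drug is held if they are not met, while the dose table is introduced as recommended and open to clinical judgment.

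**Conclusion.** The tablet count in Section 5 is wrong as written: 800 mg requires four of the supplied tablets a day, and one would give 25% of the dose. This rests only on the strength in Section 8, which the 600 mg and 400 mg levels confirm. The planned dose is consistent and actual underdosing is unlikely.

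The pre-cycle limits, taken as printed, equal 0.01 neutrophils and 0.5 platelets per microliter and would hold back almost no one. Confidence here is moderate, because the unit may be a conversion fault. Even if the source does read dL, clinicians would probably infer microliter, and the Section 6 delays for Grade 4 counts and for neutropenic fever or infection would still apply.

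Neither point changes the sample size, alpha or power.

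**What to change.** In Section 5, state the regimen as 800 mg (four 200 mg tablets) once daily, and check that the patient diary and the pharmacy instructions give the same count.

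Then look at the pre-cycle limits in the source file. If they read per microliter there, nothing needs changing. If they read dL, change both to ANC ≥ 1,000/microliter and platelets ≥ 50,000/microliter, to match eligibility. No added sentence on precedence between Sections 5 and 6 is needed.

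The cost is a wording correction in a short amendment, one source-file check, and a check of the diary and pharmacy instructions. No statistical element of the design changes.

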11. All women of childbearing potential must agree to use an effective barrier method of contraception, as described in Appendix 4, during the treatment period and for at least 1 month after discontinuation of the study drug. Male subjects should use effective barrier method of contraception during the treatment period and for at least 1 month after discontinuation of the study drug (see Appendix 4).
12. Ability to understand and the willingness to sign a written informed consent document.

Exclusion Criteria

1. Grade 3B FL or evidence of transformation of FL to a more aggressive lymphoma 2.

Prior and concomitant therapy:

- a. Prior exposure to any PI3 Kinase inhibitor
- b. Exposure to chemotherapy, radiotherapy, or immunotherapy within 3 weeks prior to entering the study or lack of recovery from adverse events due to previously administered treatments.
- c. Ongoing chronic pharmacologic immunosuppression, e.g. cyclosporine, or systemic steroids that have not been stabilized to the equivalent of ≤ 10 mg/day prednisone prior to the start of the study drug.
- d. Other concurrent investigational agents during the study period.

3. Prior allogeneic stem cell transplant
4. Central nervous system lymphoma, including lymphomatous meningitis
5. Acute intercurrent illness including, but not limited to, active infection, unstable congestive heart failure, unstable angina pectoris, psychiatric illness or any social situation that would limit compliance with study participation requirements in the judgement of the investigator
6. Major surgery performed within 4 weeks of study entry
7. Pregnant or nursing women
8. Active concurrent malignancy (except non-invasive non-melanoma skin cancer, carcinoma in situ of the cervix, or prostate intraepithelial neoplasia). If there is a history of prior malignancy, the patient must be disease-free for ≥ 3 -years at the time of study entry.
9. Documented Human Immunodeficiency Virus (HIV)-infection
10. Active hepatitis A, hepatitis B, or hepatitis C infection (see Appendix 5).
11. History of tuberculosis treatment within 2 years of study entry
12. Administration of a live vaccine within 6 weeks of first dose of study drug
13. Unable to receive prophylactic treatment for pneumocystis, herpes simplex virus (HSV), or herpes zoster (VZV) at screening
14. Prior surgery or gastrointestinal dysfunction that may affect drug absorption (e.g., gastric bypass surgery, gastrectomy)

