Colony stimulating factors (i.e., filgrastim, peg-filgrastim, and sargramostim) may be used according to the 2006 American Society of Clinical Oncology (ASCO) guidelines.(Smith et al., 2006) Peg-filgrastim should only be used if the time to the next dose is ≥ 14 days. Anemia may be managed with erythropoiesis stimulating agents according to the ASCO/ASH guidelines.(Rizzo et al., 2010) Patients with pre-existing chronic anemia treated with epoetin or darbepoietin, may continue to receive such agents during the study period, but should not start them once on study.

- Specific supportive care issues:
 - **Diarrhea:** Diarrhea should be treated promptly with appropriate hydration and antidiarrheal agents such as loperamide. Loperamide should not be taken prophylactically. Patients should be instructed to begin taking loperamide at the first sign of: 1) poorly formed or loose stool, 2) occurrence of more bowel movements than usual in one day or 3) unusually high volume of stool. Loperamide should be taken in the following manner: 4 mg at first onset of diarrhea, then 2 mg after each non-formed stool. The daily dose of loperamide should not exceed 16 mg/day. Loperamide should be deferred if blood or mucus is present in the stool or if diarrhea is accompanied by fever. In this setting, appropriate diagnostic microbiologic specimens should be obtained to exclude an infectious etiology. If the treating physician diagnoses the diarrhea as grade 3 or 4 by CTCAE v4.0, TGR-1202 should be held. If colitis is suspected colonoscopy should be considered if it can be done safely.
 - **Nausea/emesis:** Nausea and emesis should be treated with standard anti-emetics, including 5-hydroxytryptamine 3 serotonin receptor (5-HT3) antagonists, prochlorperazine, metoclopramide, or benzodiazepines. Patients should be encouraged to maintain adequate oral fluid intake during therapy. Dexamethasone should not be administered as an antiemetic.
 - **Anemia:** Treatment with TGR-1202 can cause anemia. Transfusions or erythropoiesis stimulating agents may be utilized as clinically indicated for the treatment of anemia and should be clearly noted as concurrent medications. Dose modifications for anemia are outlined in section 6.3.
 - **Thrombocytopenia:** Treatment with TGR-1202 can cause thrombocytopenia. Transfusion of platelets may be used if clinically indicated. TGR-1202 dose modification guidelines for thrombocytopenia are outlined in section 6.

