 - **Neutropenia:** Neutropenia can occur during treatment with TGR-1202. Blood counts should be monitored regularly as outlined in the protocol and additional testing should be obtained when indicated, according to standard clinical practice. Colony-stimulating factors, including G-CSF, pegylated G-CSF or GM-CSF may be utilized as clinically indicated. TGR-1202 dose modifications for neutropenia are outlined in section 6.
 - **Infections:** Serious infections, including pneumonia and febrile neutropenia have been reported during treatment with TGR-1202. Any suspected infection should be promptly managed. Hospitalization should be considered when clinically appropriate.
 - **Mucositis:** stomatitis has been reported during TGR-1202 therapy. Lidocaine-containing oral solutions may be used as needed to ameliorate the symptoms thereof.

- **Tumor lysis syndrome prophylaxis:** Subjects should receive allopurinol and other treatment considered appropriate for tumor lysis prophylaxis during cycle 1 as deemed necessary by the treating physician.

Concomitant Medication Guidelines

All medications taken within 30 days of screening and medications and supportive therapies that are administered during the study must be recorded in the patient's CRF and in the source documents. Concomitant medications for other medical conditions are permitted as clinically indicated. Over-the-counter and herbal products should not be taken during the study period without prior consultation with the PI.

The following concomitant medications are prohibited during the study period:

- Any antineoplastic agent other than TGR-1202
- Prednisone at a stable dose of >10 mg daily
- Radiation therapy; palliative radiation therapy to a pre-existing symptomatic lesion may be allowed on a case-by-case basis after discussion with the study PI

Duration of Therapy

Treatment may continue until one of the following criteria applies:

- Disease progression
- Unacceptable AE(s) Withdrawal of consent
- Changes in the patient's condition that render continuation of the study drug unacceptable in the judgment of the treating physician
- An event that in the judgment of the treating physician warrants discontinuation of therapy

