Overall Response Rate (ORR) will be defined as the sum of CR rate and PR rate based on evaluation of best response in each patient.

Evaluation of Best Response

The best overall response is the best response recorded from the start of the treatment until disease progression/recurrence. The patient's best response assignment will depend on the achievement of both measurement and confirmation criteria. The best overall response will be used as the reference to define progression of disease, should this occur.

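### The on-study steroid limit names only prednisone at a stable dose above 10 mg daily, narrower than the entry rule, and no response-rate rule deals with a response first recorded during other permitted steroid use

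*Combined protocol and SAP*

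**What the plan says.** **Entry.** Exclusion 2c (Synopsis and Section 3) rules out patients on "systemic steroids that have not been stabilized to the equivalent of" 10 mg/day of prednisone or less. It covers the whole class, in prednisone equivalents, and is judged before study drug starts.

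**On study.** The prohibited list under Concomitant Medication Guidelines (Section 5) has three items. The first is "Any antineoplastic agent other than TGR-1202", the second is "Prednisone at a stable dose of >10 mg daily", and the third is radiation. The same subsection states: "Concomitant medications for other medical conditions are permitted as clinically indicated". It also requires that "medications and supportive therapies that are administered during the study must be recorded" in the CRF.

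**Other limits in Section 5.** Regimen Description says: "No investigational or commercial agents or therapies other than the study drug may be administered with the intent to treat" the malignancy. Supportive care, under nausea and emesis, says: "Dexamethasone should not be administered as an antiemetic".

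**Endpoint.** In Section 11, ORR is the CR rate plus the PR rate by best response, and best overall response is the "best response recorded from the start of the treatment until disease progression/recurrence". The next sentence makes the assignment depend on measurement and on confirmation criteria. Confirmation is not defined there or in Section 13.

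**The concern.** A patient who could not have enrolled on a given steroid dose could start that dose after day 1 without breaking the prohibited list, provided that the drug is not prednisone or the dose is not stable, and that the reason is neither lymphoma nor, for dexamethasone, nausea. The entry rule shows that the plan can express the limit in equivalents, so the on-study line looks like a drafting slip.

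The trial has one arm, and ORR is its only tested endpoint. If a response is first recorded during a steroid course, no comparison within the trial can show how much of it is due to TGR-1202. The plan has no rule that sets such a response aside or flags it.

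**Working it through.** **1. Does another rule close the gap?**

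| Rule | Reaches | Leaves open |
|---|---|---|
| Exclusion 2c | All systemic steroids, in equivalents | Anything started after the first dose |
| Prednisone item | Prednisone above 10 mg daily, stable dose | Other steroids; bursts and tapers |
| Nausea/emesis text | Dexamethasone as an antiemetic | Other indications |
| Regimen Description | Agents given to treat the malignancy | Non-lymphoma use |
| Antineoplastic item | Not clearly steroids, since prednisone has its own dose limit in the next line | Steroids for other conditions |

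What remains is systemic steroids for non-lymphoma conditions, other than dexamethasone for nausea and stable prednisone above 10 mg.

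**2. Can such use overlap dosing?** It can. Section 7 lists rash as very common (10% or more) and colitis as common (1% to under 10%). Section 6 keeps the dose unchanged for non-hematologic events of grade 2 or lower, and withholds drug for pulmonary events of grade 2 or higher only as warranted. Other facts point to few overlaps. Phase I grade 3/4 diarrhea was 1% (Section 2). Section 6 calls pneumonitis minimal, withholds drug for other non-hematologic events of grade 3 or higher, and ends treatment when an interruption exceeds 28 days. The frequency of steroid use is not given.

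**3. Reproduce the design (Section 13).** Inputs are n = 20, null ORR 0.33, alternative 0.60 and one-sided error 0.10. Exact binomial:

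- P(X ≥ 9 | 0.33) = 0.182, above 0.10.
- P(X ≥ 10 | 0.33) = 0.0866, so the boundary is 10 of 20.
- P(X ≥ 10 | 0.60) = 0.8725, which matches the stated 87%.

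**4. Illustrate the effect.** Assume that *m* patients are exposed and that steroids turn a share *c* of their non-responses into recorded responses. Each exposed patient then responds with probability 0.33 + 0.67*c*, and the other 20 − *m* with 0.33. For *m* = 1, P(X₁₉ = 9 | 0.33) = 0.0782, so the false-positive rate is 0.0866 + 0.67 × 0.0782 × *c* = 0.0866 + 0.0524*c*.

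| *c*, with *m* = 1 | False-positive rate |
|---|---|
| 0 | 0.087 |
| 0.10 | 0.092 |
| 0.25 | 0.0997 |
| 0.50 | 0.113 |
| 1 | 0.139 |

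The planned 0.10 is passed when *c* exceeds (0.10 − 0.0866)/0.0524 = 0.256 with one exposed patient. The same calculation gives 0.125 with two and 0.082 with three. If the trial lands exactly on the boundary, reclassifying one response moves 10/20 (p = 0.087) to 9/20 (p = 0.182). Every *m* and *c* here is an assumption.

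**5. Why not change the primary analysis?** At a true ORR of 0.60, suppose that one exposed patient's true response loses credit with probability 25%, 50% or 100%. The chance of reaching 10/20 falls from 0.872 to 0.858, 0.843 or 0.814.

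**6. Does a later-scan rule fit the schedule?** Scans fall at the end of cycles 2 and 6, which are 4 × 28 = 112 days apart when no doses are held. After cycle 6, Section 11 sets the next scan 4 months later, or 6 months later after a CR.

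**The case against.** - **The causal step is assumed.** A steroid given for another condition would have to produce at least a PR at a scheduled scan. Section 2 shows prednisone only inside multi-drug regimens and gives no single-agent steroid response rate in FL. Exclusion 2c groups steroids with immunosuppressants, so its purpose may not be to protect the response endpoint. This stands, and it is why no size can be claimed.
- **Confirmation.** A reader might infer that any response first seen on steroids simply counts toward ORR. The documents do not support that, because Section 11 makes best response depend on confirmation criteria. Those criteria are undefined, so they cannot be relied on to remove such a response either.
- **The word stable.** It can be read as an echo of the entry rule, barring sustained use and leaving short courses to clinical judgment. That is a fair reading, but sustained use of another steroid remains open, and so does the handling of responses.
- **The data are already collected.** Medication records would let anyone list overlaps among 20 patients. This is true, but a rule chosen after the responses are known is weaker than one stated in advance.
- **The rewording exempts the likeliest use**, a short course for an adverse event. This also stands, so the rewording needs the sensitivity analysis beside it.

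**Conclusion.** The point holds as a minor one. Apart from dexamethasone for nausea and anything given to treat the lymphoma, the on-study limit covers only prednisone at a stable dose above 10 mg daily. It is narrower than exclusion 2c, and no ORR rule sets aside a response first recorded during other steroid use.

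A reader might go further and infer that non-prednisone steroids are unrestricted on study, or that the ORR test will exceed its error rate. The documents support neither. The antiemetic and treatment-intent rules restrict some use. The false-positive figures rest wholly on assumed exposure and conversion, and with one exposed patient the planned 0.10 is passed only if conversion exceeds about 26%. The effect is probably small. The reason to act is that the change costs very little.

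**What to change.** 1. Reword the prednisone item to match exclusion 2c: *systemic corticosteroids at more than 10 mg/day prednisone equivalent, except short courses for adverse events of a stated maximum length*.
2. Keep the primary ORR unchanged. Add one sensitivity analysis from CRF medication data. It counts as non-response any CR or PR first recorded during systemic steroids above that dose, or within a pre-stated window after them, unless the response is still present at a later scheduled scan off steroids. A window of 28 days (one cycle) is an example; the documents give no duration of steroid effect.

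**Cost.** One reworded line and one extra analysis of data already required, with no added visits or scans. The medication rule becomes slightly tighter. The sensitivity analysis may discard some true responses, especially those first seen at or after cycle 6, where the next scan is 4 to 6 months away and a patient may stop before it.
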